8. Subjects who have a condition or general disability or infirmity that in the opinion of the investigator precludes further participation in the study
9. Subjects with an ostomy

Study Calendar	Screening	Remaining Hospitalization	30 Day Follow-up
Enrollment Criteria	x	x	
Study Group Assignment	x		
Informed Consent	x		
History and Physical	x		
Collection of demographic data	x	x	
Monitoring for return of bowel function		x	
Administration of Entereg 12mg PO BID or conservative management		x (until return of bowel function)	
Enhanced Recovery Program (ERP)		x	
Complications/ Adverse events		x	x

Recruitment

Patients will be recruited from the University Hospitals Case Medical Center Division of Colorectal Surgery in Cleveland, OH. The patient population in this study will be candidates of either sex, over 18, who have benign or malignant colonic or rectal disease in which resection was performed via an open or laparoscopic approach, small bowel resection or ileostomy reversal with small bowel resection and primary anastomosis and subsequently developed postoperative ileus. The diagnosis of postoperative ileus will be made by meeting one or more of the following criteria: 1) return to NPO status after initial attempts at oral diet, 2) placement of nasogastric tube after surgery. Patients will be recruited until at least 142 participants are enrolled unless the study is halted prematurely by the safety monitoring board. The investigators will discuss the study with potential subjects prior to surgery date. The potential subjects will be given an information sheet to provide information about the study prior to surgery as part of their pre-op packet. This will give patients an opportunity to review information on the study in the event they are diagnosed with an ileus and approached to participate.

Enrollment and Consent

Enrollment will take at the time of diagnosis of postoperative ileus. The patients will be asked to participate in the study after evaluation by either the PI or the co-investigators. The investigator and study coordinator will discuss the study with the patient and informed consent will be obtained. Patients will be assigned a unique study identification number.

Randomization

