Randomization will take place following enrollment and consent. A numbered, sealed envelope, corresponding to the patients' assigned study number, will be opened by *the study coordinator* indicating to which study group the patient is randomized. The study coordinator will notify the pharmacy which study group the patient has been randomized to. Randomization will be stratified to open or laparoscopic surgery, location of surgery (right/left), stoma reversal and presence or absence of stoma. *This will be kept in a locked key to be revealed at the end of the study.*

Enhanced Recovery After Surgery Pathway

All patients will be managed via standardized accelerated postoperative recovery guidelines, which are currently in use by the division of colorectal surgery at UHCMC. This includes patient-controlled analgesia pump, oral analgesia and diet on the first postoperative day, early postoperative ambulation, and defined discharge criteria.

Study Methods

At the time of diagnosis of postoperative ileus and after enrollment and randomization, all patients will be returned to NPO status. Nasogastric tubes (NGT) may be placed for gastric decompression at the discretion of the surgical team if clinically indicated. In the event that an NGT is placed, medications will be given orally or via the NGT, which will be clamped for 30 minutes after administration. Patients will continue on standard ERAS pathways with the exception of reduction of diet. Antiemetics will be given as clinically indicated; however, no prokinetic or promotility agents will be given as scheduled dosages.

Patients randomized to the study group will be given 12mg of Entereg orally twice a day, from the time of diagnosis of postoperative ileus to the time of return of bowel function and tolerating solid food without vomiting or experiencing significant nausea within 4 h following the meal, or without having to revert to enteral fluids only or for 5 days.

Patients randomized to the control group receive standard postoperative care.

The patient and surgical team will be able to know which arm of the study the patient is in based on documentation in the medical record of the administration of Entereg.

Patients in both groups will remain NPO until the return of bowel function, defined as passage of stool, decrease in nasogastric tube output. At this point, the nasogastric tube will be removed and a trial of oral diet will be attempted per surgeon's discretion.

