Standard discharge criteria will be applied to all patients, including:

- Passage of stool
- Ability to tolerate solid food and to drink comfortably
- Adequate oral analgesia
- Patient's willingness to be discharged.

Data to be collected

The medical/surgical information below will be collected as part of this research study and is all information already available as part of the patients medical chart.

- Patient name, medical record number
- Past Medical History

- Past Surgical history
- Preoperative Medications (including steroids, anticoagulation, opioid use)
- Pre-operative Diagnosis
- Patient Demographics (age, gender, BMI, ASA score)
- Procedure performed
- Time of surgery
- Wound classification
- Estimated blood loss
- Intraoperative transfusion
- Intraoperative IV fluids given
- Conversion from laparoscopic to open procedure
- Stoma creation
- Time/day surgery to ileus
- Time from surgery to medication given
- Time from ileus diagnosis to medication given
- Was there return of bowel function (flatus or stool, solid or liquid, stoma output) prior to ileus
- Intra-abdominal infection/anastomotic leak
- Time/day of return of bowel function post ileus (flatus and stool- solid or liquid, and stoma function)
- Time/day of ability to tolerate oral diet (liquid and solid food)
- Nasogastric tube placement and daily output
- Duration of nasogastric tube
- Use and type of anti-emetics given
- Total number of Entereg doses given
- Post operative complications including reoperation
- Length of stay in hospital, defined as time from surgery to discharge
- 30-day readmissions

The above collected data will be put into a REDCap (Research Electronic Data Capture) database which is a secure web application for managing online surveys and databases. It allows the safe and secure storage of research data including storage of PHI HIPAA identifier fields.

Study Completion

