- Intraoperative IV fluids given
- Conversion from laparoscopic to open procedure
- Stoma creation
- Time/day surgery to ileus
- Time from surgery to medication given
- Time from ileus diagnosis to medication given
- Was there return of bowel function (flatus or stool, solid or liquid, stoma output) prior to ileus
- Intra-abdominal infection/anastomotic leak
- Time/day of return of bowel function post ileus (flatus and stool- solid or liquid, and stoma function)
- Time/day of ability to tolerate oral diet (liquid and solid food)
- Nasogastric tube placement and daily output
- Duration of nasogastric tube
- Total number of Entereg doses given
- Post operative complications including reoperation
- Length of stay in hospital, defined as time from surgery to discharge
- 30-day readmissions

Statistical Methods

The study co-investigators and research team will perform statistical analysis. Routine statistical analyses will be utilized for parametric and non-parametric datasets, as appropriate. Demographic data will be analyzed using students t-test or Fishers exact test as appropriate. Categorical data will be analyzed using χ^2 analysis or Fishers exact test where applicable. Normally distributed data will be presented as means \pm SD of the mean, non-normally distributed data will be presented as medians \pm quartiles and categorical data will be presented as raw data and frequencies. A p value of < 0.05 will be considered statistically significant.

Power/Sample Size:

In our practice, patients undergoing open or laparoscopic colectomy without stoma creation who develop POI have a mean length of stay of 10.67 +/- 5.98 days compared to 4.86 days for patients who do not develop POI.

Using this information, to detect a significant decrease in length of stay by 3 days, with a 0.05 level of significance and a power of 80%, a total of 142 patients (71 patients per arm) are required.

Drug supplies (Entereg) for this study will be provided by Merck.

In the event that Merck is unable to provide drug supplies, the University Hospitals Case Medical Center Pharmacy will provide Entereg for this study.

The University Hospitals Case Medical Center Pharmacy will be responsible for distribution of drug in the treatment arm.

All adverse events will be reported per local IRB policy.

Reportable Problem: Any event which meets all three of the following criteria:

- Unexpected (in relation to the protocol and informed consent document),

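### The stratification factors enter no named analysis of length of stay, which may cost precision, and the stoma and location factors do not fit the eligibility criteria

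*Combined protocol and SAP*

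**What the plan says.** The Randomization section sets four factors: "Randomization will be stratified to open or laparoscopic surgery, location of surgery (right/left), stoma reversal and presence or absence of stoma". Each sealed envelope is numbered to match the patient's study number. Neither blocks nor a separate sequence per stratum is described.

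The Study Overview makes hospital length of stay the primary outcome. Statistical Methods offers only a general sentence that could cover it: "Routine statistical analyses will be utilized for parametric and non-parametric datasets, as appropriate". That section assigns the t-test or Fisher's test to demographic data, and chi-squared or Fisher's test to categorical data. No model, covariate or stratified test appears anywhere.

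Power/Sample Size works from a difference in means. It reports that "patients undergoing open or laparoscopic colectomy without stoma creation who develop POI have a mean length of stay of 10.67 +/- 5.98 days", and requires 142 patients (71 per arm) "to detect a significant decrease in length of stay by 3 days" at the 0.05 level with 80% power.

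On eligibility, item 9 of the Exclusion criteria reads "Subjects with an ostomy", with no time point. Under Enrollment and Consent, "Enrollment will take at the time of diagnosis of postoperative ileus", which is after surgery. Besides colorectal resection, Recruitment admits "small bowel resection or ileostomy reversal with small bowel resection and primary anastomosis and subsequently developed postoperative ileus". The lists under Data to be collected and Variables/Time Points of Interest both include "Stoma creation" and stoma function after ileus.

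**The concern.** When the arms are balanced on factors that predict the outcome and the analysis ignores those factors, the variance they explain stays in the error term. The primary interval is then wider, and power lower, than the design allows. The Study Methods let the surgical team know the arm, and the study team analyses the data, so the unnamed length-of-stay analysis is also an open choice that is better closed in advance.

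Two of the factors also fit poorly with who may enter. The text does not settle whether patients with a new stoma are in the trial. A patient with an isolated small bowel resection has no defined location stratum, so whoever assigns the envelope must improvise. Both points have to be settled before the factors can enter any model.

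**Working it through.** **1. The plan's own figure.** Inputs from Power/Sample Size: difference 3 days, SD 5.98, alpha 0.05 (sidedness not stated; two-sided assumed), power 80%.

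n per arm = 2 × (1.960 + 0.842)² × (5.98/3)² ≈ 62.4, so 63 per arm and 126 in total. The t-based solution is 63.35, so 64 per arm and 128 in total. The stated 142 is not reproduced; it is larger than these inputs need. A 10% dropout allowance would give 128/0.9 = 142.2, but none is stated. At 71 per arm, power is 84.8% (t-based 84.3%).

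**2. Formulas, normal approximation.** SE = 5.98 × √(2/71) = 1.004 days, so the unadjusted 95% half-width is 1.96 × 1.004 = 1.967 days. Adjustment multiplies the SE by √(1 − R²). If allocation is restricted within strata, the unadjusted estimate truly varies with this smaller SE, but the test still uses the larger one:

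- unadjusted type I error = 2 × [1 − Φ(1.96/√(1 − R²))]
- unadjusted power = 1 − Φ[(1.96 − 3/1.004)/√(1 − R²)]
- excess interval width = 1/√(1 − R²) − 1

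R² is not in the documents; 0% to 20% is assumed.

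| R² | Adjusted half-width (days) | Excess width | Unadjusted type I error | Unadjusted power | Adjusted power |
|---|---|---|---|---|---|
| 0 | 1.967 | 0 | 0.050 | 0.848 | 0.848 |
| 5% | 1.917 | 2.6% | 0.044 | 0.8545 | 0.8658 |
| 10% | 1.866 | 5.4% | 0.039 | 0.861 | 0.883 |
| 20% | 1.759 | 11.8% | 0.028 | 0.875 | 0.9165 |

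**3. Simulation with restricted allocation.** 142 patients, 8,000 runs per setting, blocks of 4, normal or skewed (skewness 2) errors, main-effects model. Two assumed layouts were used, with 6 and 10 strata; ranges are over layout and error type.

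| R² | Unadjusted type I error | Excess width | Unadjusted power | Adjusted power |
|---|---|---|---|---|
| 0 | 0.047–0.055 | 0 | 0.841–0.849 | 0.841–0.849 |
| 5% | 0.043–0.050 | 2.4–2.6% | 0.841–0.848 | 0.850–0.859 |
| 10% | 0.040–0.042 | 5.3–5.5% | 0.855–0.859 | 0.876–0.880 |
| 20% | 0.028–0.031 | 11.7–12.0% | 0.858–0.874 | 0.903–0.918 |

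Within a setting, the power loss is 0.9 to 1.2 points at R² 5%, 2.1 to 2.2 at 10% and 3.9 to 4.5 at 20%. The adjusted test keeps a type I error of 0.048 to 0.055. A separate run with 8 strata agrees: 85.6% against 88.4% power at R² 10%, and 86.6% against 91.0% at 20%.

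**4. Without restriction within strata.** The unadjusted type I error is 0.044 to 0.054, which is nominal. Adjustment changes power by −0.5 to −1.4 points at R² 0, +0.3 to +1.1 at 5%, +2.4 to +2.8 at 10% and +5.4 to +7.0 at 20%.

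**5. The loss in patients.** Matching the adjusted width without adjusting needs 142 × (ratio² − 1) more patients: 142 × (1.025² − 1) ≈ 7 at R² 5%, 142 × (1.054² − 1) ≈ 16 at 10%, and 142 × (1.118² − 1) ≈ 35 at 20%.

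**6. Exclusion 9 against the stoma factors.**

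- Ostomy at enrolment: the stoma-present level is empty. Of 2⁴ = 16 nominal cells (142/16 = 8.9 patients on average), 8 disappear.
- Ostomy before surgery: the ileostomy-reversal patients admitted by inclusion criterion 1 are removed, and the reversal factor is constant.
- Either: both stoma factors are constant.

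Every reading contradicts some other part of the protocol.

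**7. Location against eligible procedures.** Small bowel resection is listed apart from colorectal resection and from reversal, so it is neither right nor left and is not covered by the reversal factor. Reversal has its own factor, but the text does not say that location is then skipped.

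**The case against.** The strongest reply is that the loss is conditional at every step. R², the stratum shares and the block size are all assumed, and the larger figures (12%, 35 patients) come from the top of the assumed range. The unadjusted comparison is itself inferred, because the plan names no length-of-stay test at all. All of this stands, so the loss can only be called possible.

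A reader might infer more than the documents support:

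- That the unadjusted test is conservative. This needs restriction within strata, which the Randomization section does not state. Envelopes tied to study numbers, with no sequence per stratum described, leave it open. Without restriction the type I error is nominal, although adjustment still gains power when the factors are prognostic.
- That the primary analysis would be invalid or the trial underpowered. It would be neither: unadjusted power is about 84% to 87% over the assumed range, against 80% planned.
- That the stoma conflict misallocates patients. An empty level misallocates nobody, and recording stoma creation from the chart does not by itself make those patients eligible. What remains is contradictory wording about who is in the trial.
- That total or subtotal colectomy is a stated gap. The documents never mention it; only small bowel resection is explicitly eligible and without a level.

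It is also fair to say that a linear model in days is partly a preference, since Statistical Methods leaves non-parametric methods open. The sizing is a mean difference in days, however, and the simulations with skewed stay kept the adjusted error rate near 5%.

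**Conclusion.** The point holds as a recommended improvement. Four factors are used to randomise and none appears in a named analysis of the primary outcome. Under the stated SD and sample size, ignoring them under blocked allocation costs nothing if they are not prognostic, and about 1, 2 or 4 power points with intervals about 2.5%, 5% or 12% wider at R² of 5%, 10% or 20%. These figures rest on the assumed R², stratum shares and blocks of 4. Planned power is met with or without adjustment.

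The inconsistencies over exclusion 9 and over the location of small bowel resection are in the text itself and need no assumption.

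**What to change.** - **Primary analysis.** Name a linear model for length of stay in days, with treatment and main effects for the stratification factors actually used. Report the adjusted mean difference with its 95% CI. Use main effects rather than cell indicators, because some cells will be small. Add a log-scale or van Elteren sensitivity analysis for skew.
- **Allocation.** State whether allocation is restricted within strata, and how the numbered envelopes achieve it.
- **Stoma.** Reconcile exclusion 9 with the inclusion criteria, Recruitment, the stratification sentence, the sizing population and the stoma data items. Drop any factor that is then constant.
- **Location.** Give small bowel resection, and any other eligible procedure that is neither right nor left, a defined level, and say how reversal is placed. Keep the levels few: in the assumed 10-stratum layout the smallest expected cell is 4.5 patients.
- **If envelopes are already in use.** Model the factors as randomised, and add procedure type from the collected data as a baseline covariate.

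The cost is SAP wording and a protocol clarification, plus a revised envelope list if enrolment has not begun. No extra patients or data are needed. The model spends about 3 to 5 degrees of freedom, and up to about 1.4 power points if the factors are not prognostic and allocation is not effectively stratified.

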This will be a prospective randomized control trial with a total of 142 patients. Patients who undergo laparoscopic or open colorectal resection, small bowel resection, or ileostomy reversal with small bowel resection that subsequently develop postoperative ileus will be eligible for enrollment. If they meet inclusion/exclusion criteria, they will be randomized at the time of diagnosis of postoperative ileus to receive Entereg as rescue therapy or to receive conservative standard care.

Patients randomized to the Entereg group will be given 12mg of Entereg two times daily from the time of randomization until the return of bowel function or 5 days. Both groups will be treated with conservative standard care, including bowel rest, reduction in oral diet, and placement of nasogastric tube as clinically indicated.

All patients will follow a standard ERAS pathway after surgery, with early feeding and ambulation, along with opioid minimizing measures as is our standard postoperative protocol.

Primary outcome will be hospital length of stay.

Secondary outcomes will include time to return of bowel function, 30-day morbidity/mortality, complications, reoperation and readmission.

Total number of patients: 142

Patients in each study group: 71

Inclusion criteria

1. Subjects who have benign or malignant colonic or rectal disease that have undergone laparoscopic or open colorectal resection, small bowel resection or ileostomy reversal with small bowel resection and subsequently developed postoperative ileus, defined as:
 - a. Return to NPO status after initial diet attempts, or
 - b. Placement of nasogastric tube
2. Subjects who are 18 years of age and older
3. Subjects of either gender
4. Subjects who are willing and able to adhere to protocol requirements, agree to participate in the study program and provide written and informed consent.

Exclusion criteria

1. Subjects who received Entereg preoperatively.
2. Subjects that have taken therapeutic doses of opioids for more than 7 days immediately prior to surgery.
3. Subjects with severe hepatic impairment.
4. Subjects with end-stage renal disease.
5. Subjects who are pregnant.

6. Subjects who were diagnosed with a complete small bowel obstruction preoperatively.
7. Subjects with a medical condition that may interfere with the use of the study medication Entereg.

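### Cheap improvement, not an error: length of stay could be adjusted for time from surgery to ileus (already collected) and for nasogastric tube status at randomisation (needs one clean field)

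*Combined protocol and SAP*

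**What the plan says.** **Outcome and time origin.** Study Overview makes hospital length of stay the primary outcome and places randomisation at the diagnosis of ileus. Data to be collected counts stay from surgery to discharge and separately lists the time or day from surgery to ileus.

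**Qualifying for the trial.** Under Recruitment, "The diagnosis of postoperative ileus will be made by meeting one or more of the following criteria": return to nil by mouth after diet attempts, or "placement of nasogastric tube" after surgery. The inclusion criteria give the same two routes.

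**Randomisation.** "Randomization will be stratified to open or laparoscopic surgery, location of surgery (right/left), stoma reversal and presence or absence of stoma". Tube status is not a factor.

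**Tubes after randomisation.** Study Methods: "Nasogastric tubes (NGT) may be placed for gastric decompression at the discretion of the surgical team if clinically indicated". The same section states: "The patient and surgical team will be able to know which arm of the study the patient is in".

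**Tube data.** The two data lists contain "Nasogastric tube placement and daily output" and the tube's duration. Neither lists tube status at randomisation, a placement time, or the ileus criterion met. The Study Calendar has a row for "Enrollment Criteria" at screening.

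**Analysis.** Statistical Methods refers to routine parametric and non-parametric analyses and names t, chi-square and Fisher's exact tests. It names no covariate or adjusted model, and no specific test for length of stay.

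**The concern.** Two pieces of pre-randomisation information bear on length of stay, and the plan uses neither.

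The first is time from surgery to ileus. Each patient's stay is the sum of the days before diagnosis and the days after it. Entereg starts after diagnosis and can act only on the second part. Variation in the first part adds noise to an unadjusted comparison unless it is offset by an opposite relation with the second.

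The second is tube status at randomisation. The protocol suggests why it may matter: the tube comes out at return of bowel function, oral diet is tried only then, and tolerating solid food is a discharge criterion. It gives no figures for the link.

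At stake are a little precision and some protection against chance imbalance. There is also a practical trap. Tubes can be placed after randomisation by a team that can know the arm, and the background section reports an impression that Entereg reduces tube placement. A later analysis on whether a patient was ever tubed could therefore condition on a consequence of treatment.

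**Working it through.** **1. The plan's own figure.** Inputs from Power/Sample Size: effect 3 days, SD 5.98, alpha 0.05 (taken as two-sided), power 80%.

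n per arm = 2(1.960 + 0.842)² × 5.98² / 3² = 62.4, so 63; the t-test version gives 64. The stated 71 per arm is larger. An allowance of about 10% would explain it (64 × 1.1 = 70.4), but none is stated. That is a separate matter. Here it means that power at 71 per arm is 84.3% (noncentral t), not 80%.

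**2. Time from surgery to ileus.** Write stay = A + B, with A the days from surgery to diagnosis and B the days from diagnosis to discharge. In a linear model for stay in days that includes A, the estimated arm effect is the same whether the outcome is A + B or B, so adjustment removes the noise that A contributes. If A is unrelated to B, the variance removed is R² = SD(A)²/5.98². The documents do not give SD(A). As an assumed illustration:

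- SD(A) = 1 day: R² = 1/35.76 = 0.028, power 85.3%.
- SD(A) = 2 days: R² = 4/35.76 = 0.112, power 88.3%.

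If late ileus goes with a shorter remaining stay, the gain is smaller and could vanish. If it goes with a longer one, the gain is larger.

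**3. Baseline tube status.** Neither the tubed share p nor the stay gap g is in the documents. Assume p from 20% to 50% and g from 1 to 4 days. Then R² = p(1 − p)g²/5.98², residual SD = 5.98√(1 − R²), with 139 degrees of freedom.

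| Tubed | g = 1 | g = 2 | g = 3 | g = 4 |
|---|---|---|---|---|
| 20% | 84.5% | 85.0% | 85.8% | 86.9% |
| 30% | 84.6% | 85.2% | 86.2% | 87.7% |
| 50% | 84.6% | 85.3% | 86.6% | 88.3% |

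R² runs from 0.0045 to 0.112. Multiplied by 142, that is worth about 1 to 16 patients. The top figure needs both half the patients tubed and a 4-day gap. With a gap of 1 to 2 days the gain is at most 85.3 − 84.3 = 1.0 point.

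**4. Chance imbalance in tube status.** Take the tubed counts in each arm as independent Bin(71, p), unrelated to the stratification factors. An Entereg-arm excess of 10 or more has probability 5.5% (p = 50%), 4.1% (30%) or 2.3% (20%). With half tubed, the chance in either direction is 11%. An excess of exactly 10 shifts the estimate by 10/71 × g = 0.14 to 0.56 days. With half tubed and g from 1 to 4, conditional power is:

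- Unadjusted, excess in the Entereg arm: 81% down to 68%.
- Unadjusted, excess in the control arm: 88% up to 95%.
- Adjusted, either direction: 84% to 88%.

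These are tail cases, already averaged into the 84.3%.

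**5. Why not a further stratum.** Four two-level factors give 2⁴ = 16 nominal cells, or 8 if the exclusion "Subjects with an ostomy" empties the stoma-present level. Adding tube status gives 32 or 16 cells: 142/32 = 4.4 or 142/16 = 8.9 patients each.

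**The case against.** The strongest case against is that nothing planned is wrong without these covariates. Randomisation makes the unadjusted comparison valid, the power target is exceeded, and the tube effect is assumed. The larger figures come from the most favourable corner of the assumptions, and imbalance is as likely to favour Entereg as to hurt it. All of this stands and sets the grade.

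A second objection is that the missing baseline field harms no planned analysis, because none conditions on tube status. The data lists are headings rather than the case report form. Dated daily output, time to ileus or the screening check of eligibility may recover approximate status. This largely stands; what remains is a tube placed later on the day of randomisation.

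A third is that a stratified rank test crossing tube status with the randomisation factors would bring back sparse cells and could lose power, and that choosing the test after seeing skew leaves the primary analysis data-dependent. That is right, and the fix avoids both.

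A reader might infer more: that leaving tube status out of the stratification is a flaw, that the result would be biased, or that the trial is underpowered. The documents support none of these. The stratification already has many cells, randomisation protects the comparison, and the stated inputs give more than 80% power.

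**Conclusion.** The point holds as an optional, low-cost improvement. The firmer part is time from surgery to ileus: by the protocol's own definitions it is a component of the outcome, it is fixed before allocation, and it is already collected. The size of its benefit is unknown, because the documents give neither its spread nor its relation to the remaining stay. Baseline tube status is the weaker covariate; its link with stay is plausible but undocumented. Under the assumed ranges, adjusting for it lifts power from 84.3% to somewhere between 84.5% and 88.3%. These figures rest on a normal linear model with SD 5.98, a 3-day effect and 71 patients analysed per arm. The case for recording tube status at randomisation rests as much on keeping it distinct from later, arm-aware placement as on the power gained.

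**What to change.** - Leave the stratification as it is.
- At randomisation, record whether a tube is in place and which ileus criterion was met. Record the date and time of any later placement.
- Prespecify one linear model for length of stay with arm, time from surgery to ileus and baseline tube status, keeping all patients as randomised.
- Settle the handling of skew in advance: robust standard errors, which keep the effect in days, or a log scale, which turns it into a ratio.
- If a rank test is wanted as a sensitivity analysis, stratify it on tube status alone, not crossed with the randomisation factors.
- Never adjust for, or subgroup on, whether a patient was ever tubed.

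The cost is two or three extra data items, which the chart or the randomisation visit should supply, and a slightly more complex analysis. The downside is that the average gain is modest, and from tube status it is at most about 1 point of power if tubed patients stay only 1 to 2 days longer.
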